#### **2.3.13 Number of patients who have had repeat parathyroidectomy (PTx) procedure**

Number of patients with repeat PTx procedure performed after the current procedure [Time Frame: 6 - 12 months after PTx procedure.]

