## PROTOCOL SUMMARY

Title	Evaluating Impact of Near Infrared Autofluorescence (NIRAF) Detection for Identifying Parathyroid Glands during Parathyroidectomy
Principal Investigator	[name]
Study Population	Parathyroidectomy patients
Primary Objectives	The specific aim of this study is to determine if PTeye is beneficial or not for (i) intraoperative identification of parathyroid tissues, (ii) improving efficiency of parathyroid surgeries, and (iii) minimizing risk of postsurgical complications.
Study Design	Double-arm, open-label
Study Intervention	PTeye
Number of Subjects	N = 160. Each investigator will enroll 40 subjects to the PTeye group and 40 subjects to the control group.
Estimated Time to Complete Enrollment:	Approximately 2 years

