# 1 BACKGROUND

## Parathyroid Surgery

Inability of the surgeon to identify or localize the diseased PG can occur in 5 – 10% of cases resulting in failed parathyroidectomies (1, 2). As a result, persistent hyperparathyroidism can occur in these patients resulting in unnecessary repeat surgeries that may be associated with increased morbidity and costs (3, 4). Ultrasound imaging, 99mTechnetium-sestamibi scintigraphy, and computed tomography (CT) have so far demonstrated variable efficacy in preoperative localization of diseased PGs (5, 6) and may not always correlate well with the surgical field of view as observed intraoperatively. Consequently, most surgeons rely on visual identification of PGs during surgery, whereby the accuracy of PG identification is eventually determined by her/his surgical skill and experience (7, 8). When in doubt, a surgeon routinely confirms the identity of PG tissue intraoperatively by sending the specimen for frozen section analysis that typically requires a wait time of 20–30 minutes per sample (9) and has additional costs.

By easily being able to distinguish parathyroid from other tissues intraoperatively, postsurgical complications and associated costs may be reduced. The unique discovery of near infrared autofluorescence (NIRAF) in parathyroid tissues demonstrated that optical modalities that detect NIRAF can be utilized for non-invasive and label-free identification of parathyroid tissues with an accuracy as high as 97%.(10, 11) Since then, several research groups have explored the feasibility of localizing parathyroid glands using NIRAF detection with reasonable success, resulting in FDA approval for this optical technique (12). In this study, we plan to evaluate whether an FDA-approved device called 'PTeye' (AiBiomed, Santa Barbara, CA) is beneficial or not, for the surgeon and patient during parathyroid operations. The results of such a study will help us to understand and assess the true impact of optical modalities such as PTeye on (i) improving the quality and efficiency of parathyroid surgeries and (ii) minimizing risk of postsurgical complications and related expenses.

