## **2 HYPOTHESIS, OBJECTIVES, AND ENDPOINTS**

The goal of this study is to assess whether using PTeye – a NIRAF detection modality – can improve patient outcomes and reduce healthcare associated costs after parathyroid surgeries.

By being able to quickly and definitively locate parathyroid glands while in the operating room, the duration of surgical procedure could be further reduced. In addition, the number of frozen section biopsy and associated costs can be minimized. Furthermore, repeat surgeries as a result of missing a diseased parathyroid gland at the time of the initial parathyroidectomy for hyperparathyroidism could potentially be avoided.

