### **2.2.3 Persistent hyperparathyroidism or hypercalcemia (failed parathyroidectomy)**

If blood calcium with/without parathyroid hormone (PTH) has not normalized at 1st post-operative visit, calcium and/or PTH is subsequently measured as necessary. Patient is defined to have a failed parathyroidectomy if hypercalcemia/hyperparathyroidism (defined as total blood calcium level > 10.5 mg/dL or 2.6 mmol/L, with/without elevated serum intact PTH > 65 pg/ml or 6.9 pmol/L) persists at or after the 6th postoperative month. [Time Frame: 6 months after PTx procedure]

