## **Primary Completion**

The study will reach primary completion (complete enrollment) approximately 12-18 months from the time the study opens to accrual.

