### **4.1 Subject Status**

Subject statuses throughout the trial are defined as follows:

- Prescreening: preconsent (subject considering trial or study staff considering patient for the trial per institutional recruitment methods).
- Screening: period after consent, but prior to eligibility confirmation.
- Consented: consented, prior to eligibility confirmation.
- Eligible: the local investigator confirms all eligibly criteria apply.
- On study/enrolled: date eligibility is confirmed.
- On arm: date of enrollment.
- On treatment: first day treatment was given to the last day treatment was given.
- Off treatment: the last day treatment was given.
- On follow-up: from last day of treatment to the end of follow-up period.
- Off study: follow-up period completed, with no additional data gathered.
- Withdrawn: subject fully withdraws consent (i.e., refuses ALL follow-up, even survival) or is taken off study by the local principal investigator.

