## **Follow-Up Visits**

Patients will be followed for six months following parathyroidectomy. The visits will be within 5-14 days after surgery and at 6 months after surgery. The following procedures will be performed at the follow-up visit(s):

- Physical examination
- Vital signs
- Blood chemistry assessment of serum calcium, ionized calcium, parathyroid hormone (PTH) levels, and 25-OH vitamin D levels
- Concomitant medications
- History of visits to the Emergency room, hospitalization, or repeat surgery due to high calcium levels

- Documentation of postsurgical complications

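### Repeat parathyroidectomy (2.3.13) is timed at months 6 to 12, but planned follow-up and data collection stop at month 6

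*Combined protocol and SAP*

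**What the plan says.** Section 2.3.13 lists as a secondary outcome: "Number of patients with repeat PTx procedure performed after the current procedure [Time Frame: 6 - 12 months after PTx procedure".

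The Follow-Up Visits section states: "Patients will be followed for six months following parathyroidectomy". It schedules two visits, at 5-14 days and at 6 months, and repeat surgery for high calcium is one of the history items taken at them. Section 4.1 defines the end of participation: "Off study: follow-up period completed, with no additional data gathered". Section 6 also refers to follow-up data only up to 6 months.

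Two other places bear on the outcome. Section 2.2.3 declares a failed parathyroidectomy when hypercalcemia or hyperparathyroidism "persists at or after the 6th postoperative month". Section 2 names, among the events the device might help avoid, "repeat surgeries as a result of missing a diseased parathyroid gland".

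On the calendar, the Protocol Summary gives the time to complete enrolment as "Approximately 2 years", while Primary Completion says: "The study will reach primary completion (complete enrollment) approximately 12-18 months from the time the study opens to accrual". Section 3.2 puts the whole study at about two years.

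**The concern.** The outcome window begins where data collection ends. A count of repeat operations in months 6-12 would have no planned source, and a low or zero count could be taken as surgical success in both arms when the events were simply not sought.

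The gap is badly placed. Because failure is declared only at or after month 6, any reoperation prompted by that declaration comes after the last scheduled contact. Section 2.3.13 is also the only direct measure of repeat surgery, which the study hopes to reduce.

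The time frame can moreover be read in two ways. If it is the period in which operations count, those before month 6, which the visits do record, are excluded. If it is the time at which the outcome is assessed, the earlier operations count. Two analysts could report different numbers from the same data.

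**Working it through.** **Inputs**

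- Outcome window: months 6-12 (section 2.3.13).
- Planned observation: months 0-6, last visit at month 6 (Follow-Up Visits; section 6 agrees).
- Enrolment: 12-18 months (Primary Completion) or about 24 months (Protocol Summary).
- Study duration: about 24 months (sections 3.2 and 8.6), treated as an estimate and not a hard stop.
- Sample: 160 patients (Protocol Summary); 20% attrition, with 33 evaluable of 40 recruited per group (section 6).
- Failure rate: the Background puts at 5-10% the share "of cases resulting in failed parathyroidectomies". Applying it to this trial is an assumption.

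**Coverage of the window**

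- Literal reading: window 12 − 6 = 6 months; overlap with months 0-6 is 0 of 6, apart from the boundary point of the month-6 visit.
- Window taken to start at surgery: 12 months; overlap 6 of 12. Months 6-12 remain unobserved.

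**Other possible sources of data after month 6**

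Section 2.2.3 allows calcium and/or PTH to be measured as needed, but only in patients not normalised at the first postoperative visit, and it includes no check for reoperation. Section 8.6 mentions post-surgical medical history as a record to be retained; it schedules no collection. The neighbouring outcome 2.3.12 (doctor and emergency visits, admissions) runs up to 6 months, which matches follow-up. Section 2.3.13 does not.

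**Patients most likely to need repeat surgery**

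- All recruited: 0.05 × 160 = 8; 0.10 × 160 = 16.
- After 20% attrition, 0.80 × 160 = 128: 0.05 × 128 = 6.4; 0.10 × 128 = 12.8, or about 6-13.
- With the plan's own 33 of 40 per group, 4 × 33 = 132: 0.05 × 132 = 6.6; 0.10 × 132 = 13.2, or about 7-13.

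**Calendar: enrolment plus follow-up per patient**

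| Enrolment (months) | Follow-up 6 months | Follow-up 12 months |
|---|---|---|
| 12 | 18 | 24 |
| 18 | 24 | 30 |
| 24 | 30 | 36 |

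The stated two years is reproduced by 18 + 6 = 24. It is also reproduced by 12 + 12 = 24, so the duration alone does not settle which follow-up was intended. Enrolment of 24 months fits neither.

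**The case against.** The strongest reply is that the bracketed time frame says when the outcome is assessed. The definition itself sets no lower time limit, and section 2.2.3 likewise gives a 6-month time frame for a state judged at or after month 6. On that view early reoperations count, the 6-month visit records them, and a late visit would pick up a few more. This is a reasonable reading, and the figure of 0 of 6 months does depend on the literal one. It does not close the gap: the 6-month visit can record only operations already done, and nothing is scheduled after it.

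The off-study definition in section 4.1 is general status wording and would fit a 12-month follow-up equally well. That is correct. The six months rests on the Follow-Up Visits section, with support from section 6.

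The 5-10% is a failure rate, not a reoperation rate, and may not apply to patients enrolled after a failed earlier operation. That also stands: 8-16 is an assumed pool at risk, not a count of missed events.

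It can also be said that this is the last of 13 secondary outcomes and is absent from the sample size calculation. That limits the severity but does not make the outcome measurable. The enrolment discrepancy is a separate matter and is kept separate here.

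**Conclusion.** The concern holds. As written, section 2.3.13 cannot be measured over its stated window from planned data, and on either reading of the time frame repeat operations in months 6-12 would be missing. This conclusion needs only sections 2.3.13 and Follow-Up Visits, together with the absence of any later data collection in the protocol.

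How many operations would be missed cannot be derived, because the protocol gives no reoperation rate or timing. With a pool of perhaps 8-16 patients, and that only if the Background failure rate carries over, events would be few and each one missed would matter to the count. This is a secondary outcome, so the trial is not invalidated, but the mismatch should be corrected.

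The enrolment period is also stated inconsistently. Two years of enrolment leaves no room for even six months of follow-up within a two-year study.

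**What to change.** Choose one of two versions.

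1. **Follow to month 12.** Define 2.3.13 as any repeat parathyroidectomy from the index procedure through month 12. Add one 12-month medical-record check for every patient in both arms, and change the follow-up period and study duration to match. The cost is one small record review per patient, a protocol amendment with IRB approval, possibly reconsent, and a study of 24-30 months with 12-18 months of enrolment. A record check may miss operations done at other hospitals, and the protocol should say so.
2. **Stop at month 6.** Restate the time frame as the index procedure through the 6-month visit, and state that reoperations prompted by a failure declared at or after month 6 will not be captured. This changes wording only, but it gives up those events.

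The first is preferable because it observes the period in which reoperation after a declared failure would occur.

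Separately, give one enrolment period in the Protocol Summary and in Primary Completion, and set the study duration to enrolment plus follow-up.

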## **3 STUDY DESIGN**

### **3.1 General Description**

This study is a diagnostic study. Patients will be randomly allocated to the patient to the experimental arm (where the surgeon will use PTeye) or a control arm (where the surgeon will not use PTeye). Patients will be allocated via 'Random Allocation Software' (<http://mahmoodsaghaei.tripod.com/Softwares/randalloc.html>). The primary outcome of the protocol is designed to evaluate the efficacy of PTeye.

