## 6 STATISTICAL CONSIDERATIONS

Benmiloud et al. studied the impact of NIRAF-based identification of parathyroid glands which comprised of a group of 93 patients where NIRAF was used by a surgeon for parathyroid identification and a control group of 153 patients where NIRAF was not used (19). Their study reported that mean parathyroid glands identified by surgeon with NIRAF imaging was significantly higher at  $3.1 \pm 0.9$ , while that of same surgeon without NIRAF imaging was  $2.6 \pm 0.1$  ( $p=0.0001$ ). Based on this data (mean difference: 0.5 and standard deviation: 1.0), it was determined that in order to observe a statistically significant difference (i.e. for an expected mean difference: 0.7 and expected standard deviation: 1.0), 33 patients would be required per group (for a 95% powered study). Since this study may involve patient follow-up for data up to 6 months after surgery, we will thus assume an approximate data attrition rate of 20%, thus requiring a recruitment of 40 patients per group. Therefore, a total of 80 patients (study and control arm) should be recruited per surgeon for this study at this study site.

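### The trial is sized and filled per surgeon, but the plan gives no mechanism for balancing arms within surgeon and does not say whether the main analysis pools surgeons or accounts for surgeon

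*Combined protocol and SAP*

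**What the plan says.** The Protocol Summary sets N = 160 in an open-label, two-arm design and adds: "Each investigator will enroll 40 subjects to the PTeye group and 40 subjects to the control group". Section 6 arrives at the same unit: "a total of 80 patients (study and control arm) should be recruited per surgeon for this study at this study site". At 80 per surgeon, 160 patients imply two surgeons; the documents do not state the number directly.

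The account of allocation is in Section 3.1. Patients go at random to surgery with or without PTeye, and the method is given as "Patients will be allocated via 'Random Allocation Software" plus a web link. Strata, separate lists, blocks, ratio and concealment are not mentioned.

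Section 6 is a single sample-size paragraph. It takes a difference of 0.5 glands (SD 1.0) from a cited study, sizes "for an expected mean difference: 0.7 and expected standard deviation: 1.0", reaches 33 per group and raises this to 40 for attrition. It names no test or model, has no surgeon term, and does not say whether the two surgeons' patients are combined.

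The Background (Section 1, Parathyroid Surgery) says that accuracy in identifying glands comes down to the skill and experience of the individual surgeon.

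**The concern.** The protocol treats the surgeon as the sizing unit and as a determinant of the outcome, and then describes neither an allocation nor an analysis that uses surgeon. Two things are left open.

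- **Allocation.** A quota of 40 + 40 per surgeon needs a mechanism. If surgeon is ignored, the arms can be unbalanced within surgeon by chance. If the quota is reached by filling cells without a concealed list, upcoming assignments may become predictable, which matters in an open-label trial.
- **Analysis.** Only a 40 v 40 comparison is powered. Without a stated rule, the choice between pooled and separate analysis, and between adjusting for surgeon or not, could be made after the data are seen. Separate analysis would halve the sample. Pooling without surgeon would give up some precision.

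**Working it through.** **Inputs.** Difference 0.7 (planned) and 0.5 (cited study), SD 1.0, 33 then 40 per group, 20% attrition, 80 per surgeon (Section 6); N = 160 and 40 + 40 per investigator (Protocol Summary); failed surgery in 5–10% of cases (Section 1). Alpha and sidedness are not stated, so two-sided 0.05 is assumed. Number of surgeons: 160/80 = 2.

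**The plan's own figure.** n per group = 2(z₀.₉₇₅ + z_power)²SD²/difference².
- 80% power: 2(1.960 + 0.842)²/0.49 = 32.04, so 33.
- 95% power: 2(1.960 + 1.645)²/0.49 = 53.04, so 54 (45 if one-sided).

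The stated 33 therefore corresponds to about 80% power, not 95%. That is a separate error, but it sets the benchmark here. For attrition, 33 × 1.2 = 39.6 gives the stated 40; 33/0.8 would give 42.

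**Balance within a surgeon's 80 patients, if allocation ignored surgeon.**
- Simple randomisation: X ~ Binomial(80, 0.5); 2·P(X ≤ 35) = 31%.
- One list balanced 80/80 overall: X ~ Hypergeometric(160, 80, 80); 2·P(X ≤ 35) = 15%.
- Quota met: imbalance zero.

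A 45/35 split costs little power. For one surgeon at 0.7, power falls from 87.9% to 87.4% (normal approximation).

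**Bias in an unadjusted pooled estimate.** If the surgeons split 45/35 and 35/45, the shift is g × (45 − 35)/80 = 0.125g, where g is the between-surgeon difference in glands found. The documents give no g. For an assumed 0.3 to 1.0 it is 0.04 to 0.125 glands. Opposite splits at least this large have probability 2 × 0.157² = 4.9% under simple randomisation. Under one list balanced overall they have the 15% above, because 45/35 for one surgeon then forces 35/45 for the other.

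**Power for gland count (two-sample t-test, two-sided 0.05).**

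| Comparison | Difference 0.7 | Difference 0.5 |
|---|---|---|
| One surgeon, 33 v 33 | 80% | 52% |
| One surgeon, 40 v 40 | 87% | 60% |
| Pooled, 64 v 64 (80 × 0.8) | 97.6% | 80% |
| Pooled, 80 v 80 | 99.3% | 88% |

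Gland count is recorded during surgery (Section 2.3.1), while the attrition allowance is justified by 6-month follow-up, so the 40 and 80 rows fit this outcome best.

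**Pooling without a surgeon term.** The SD becomes √(1 + g²/4). At an assumed g = 1 this is 1.118, and power at 0.5 with 80 v 80 falls from 88% to about 80%. That takes the surgeon mix in each arm as left to chance. If 40/40 were met exactly, only the error estimate is inflated: 1.96 × 1.118 − 0.5/√(2/80) = 2.191 − 3.162 = −0.971, a power of about 83%. At g = 0.3 the loss is under one percentage point (88.5% to 87.8%, normal approximation).

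**Primary-type outcome.** For failure of 10% v 5% (10% is the top of the Background's range; the 5% under PTeye is an assumption), power is about 13% at 40 v 40 and 22% at 80 v 80.

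**The case against.** The strongest defence is that the Protocol Summary already promises 40/40 within each investigator. Silence about blocks is not a statement of simple randomisation, and the 31% and 15% apply only if surgeon is ignored. That stands. A reader might infer that the described allocation cannot deliver 40 + 40; the documents do not support this. They show only that the means of reaching and concealing the quota is not described.

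A reader might also infer that each surgeon will be tested separately, giving 1 − 0.95² = 9.75% chance of at least one false positive, or only 0.516² = 27% chance that both tests succeed at 0.5 with 33 per group. Section 6 contains no test and no decision rule, so both figures rest on rules found nowhere in the plan. At 40 per group the second would be 0.598² = 36%.

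Nor is 40 v 40 underpowered without qualification. At the planned 0.7 its 87% passes a usual 80% target; it falls short of the stated 95% and of what the cited 0.5 would need.

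Finally, the 0.125-gland bias needs both an assumed one-gland difference between surgeons and opposite splits. It vanishes if the quota is met.

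What survives is that the plan relies on surgeon for sizing and recruitment, leaves surgeon out of the described allocation, and leaves the combination of surgeons unspecified.

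**Conclusion.** The concern holds as a gap with an inexpensive improvement available, not as a demonstrated imbalance or a planned pair of weak tests. Under two-sided 0.05 and SD 1.0, one pooled comparison raises power for gland count over a single surgeon's 40 v 40 from about 60% to 88% at a difference of 0.5, and from 87% to 99% at 0.7. With 20% attrition (64 v 64) the pooled figures are 80% and 97.6%. Adjusting for surgeon protects a further 5 to 8 percentage points at 0.5 if surgeons differ by one gland, and almost nothing if they differ by 0.3. Two surgeons is inferred from 160/80.

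The gain is confined to gland count and other secondary outcomes. A reader might conclude that pooling makes the trial strong overall. It does not: for the persistent-disease primary outcomes in Section 2.2, about 22% power at 10% v 5% remains inadequate.

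**What to change.** - **Section 3.1:** generate a separate permuted-block list for each surgeon, 40 per arm, with varying block sizes because the trial is open-label. State who holds the lists and how assignments stay concealed until a patient is enrolled.
- **Section 6:** make the main comparison one pooled analysis of all randomised patients with surgeon as a factor: a linear model for counts and times, and Mantel-Haenszel stratified by surgeon for binary outcomes. Show surgeon-specific results descriptively. State alpha and sidedness, and correct the power claimed for 33 per group.

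The cost is a protocol amendment with IRB approval (Section 7.7). No extra patients or data are needed.

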## **Primary Completion**

The study will reach primary completion (complete enrollment) approximately 12-18 months from the time the study opens to accrual.

### **3.2 Study Completion**

The duration of the study is expected to be approximately two years from the time the study opens to accrual.

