## **8.6 Study Record Retention**

The duration of the study is expected to be approximately two years and will depend on patient availability. The data acquired from this study will be preserved indefinitely, as it may influence the future development of the entire research project. However, the data will not be accessible to anyone other than the participants of this study. All original paper records, record sheets, preoperative and postoperative lab investigations, drug/medication history, post-surgical medical history, histopathological diagnoses of the investigated tissue samples, will be collectively retained by the PI or Key Study Personnel. The data of this study will be stored in a password protected computer, and only users with permission from the PI can access the data base.

The PI at each participating site is required to prepare and maintain adequate records of the disposition of study materials and case histories that record all observations and other data pertinent to the investigation on each individual administered the materials in the investigation. Case histories include the case report forms and supporting data including, for example, signed and dated consent forms. The case history for each individual shall document that informed consent was obtained prior to participation in the study.

Study documentation includes all data entry forms, data correction forms or queries, source documents, Sponsor-Investigator correspondence, monitoring logs/letters, and regulatory documents (e.g., protocol and amendments, IRB correspondence and approval, signed participant consent forms).

Source documents include all recordings of observations or notations and all reports and records necessary for the evaluation and reconstruction of the clinical research study.

The principal investigator is required to prepare and maintain adequate and accurate case histories that record all observations and other data pertinent to the investigation on each individual administered the investigational drug or employed as a control in the investigation. Case histories include the case report forms and supporting data including, for example, signed and dated consent forms and medical records including, for example, progress notes of the physician, the individual's hospital chart(s), and the nurses' notes. The case history for each individual shall document that informed consent was obtained prior to participation in the study.

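### Repeat surgery (2.3.13) is counted over months 6 to 12, but follow-up stops at month 6; separately, the enrolment period is stated two ways

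*Combined protocol and SAP*

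**What the plan says.** **Repeat surgery.** Secondary outcome 2.3.13 is the number of patients with a further parathyroidectomy after the study operation, with "Time Frame: 6 - 12 months after PTx procedure". The Follow-Up Visits text (under Section 4.9) says "Patients will be followed for six months following parathyroidectomy", with visits at 5–14 days and at 6 months. The history taken at those visits includes repeat surgery due to high calcium. Section 4.1 defines a subject as off study once follow-up has ended, with no more data collected.

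**Calendar.** The Protocol Summary gives the time to complete enrolment as "Approximately 2 years". The Primary Completion paragraph says "The study will reach primary completion (complete enrollment) approximately 12-18 months from the time the study opens to accrual". Section 3.2 says "The duration of the study is expected to be approximately two years from the time the study opens to accrual", and Section 8.6 repeats this with a qualifier: "The duration of the study is expected to be approximately two years and will depend on patient availability". Primary outcome 2.2.3 (failed parathyroidectomy) is judged at or after the sixth postoperative month.

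**The concern.** Section 2 names avoidance of repeat surgery as a hoped-for benefit of PTeye, and 2.3.13 is the outcome that would show it. An operation can be classed as failed under 2.2.3 only from month 6, so any reoperation prompted by that classification comes after the last scheduled data collection. Reoperations in months 6–12 would then be known only by chance. In an open-label trial, no rule would make that chance equal in the two arms.

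The numbers are small. Section 1 puts failed operations at 5–10% of cases, which is 8 to 16 among 160 patients. Missing even a few reoperations could change what the trial says about them.

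The enrolment figures raise a second question. If enrolment and the whole study both take about two years, the last patients operated on would have no time left to reach the 6-month primary outcome.

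**Working it through.** **1. Outcome window against follow-up.** Section 2.3.13 needs observation from month 6 to month 12 after surgery. The follow-up schedule supplies months 0 to 6. The two meet only at month 6, and Section 4.1 rules out later collection. No accrual assumption enters, so this holds for every patient under any enrolment period.

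**2. The plan's own calendar.** Upper enrolment figure (Primary Completion) plus follow-up: 18 + 6 = 24 months. This reproduces the two years in Section 3.2, with no slack. At the lower figure, 12 + 6 = 18 months.

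**3. What a stop at month 24 would cut off.** Inputs:
- enrolment period E: 12 or 18 months (Primary Completion) or 24 months (Protocol Summary);
- outcome time F: 6 months (2.2.3);
- N = 160 (Protocol Summary);
- three assumptions that the documents do not state: uniform accrual, surgery on the day of enrolment, and closure exactly at month 24.

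Share not reaching F = max(0, E − (24 − F)) / E.

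| Enrolment E | Last 6-month assessment | Share lacking the 6-month outcome |
|---|---|---|
| 12 months | month 18 | 0 |
| 18 months | month 24 | (18 − 18)/18 = 0 |
| 24 months | month 30 | (24 − 18)/24 = 25%, or 40 of 160 |

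**4. Sensitivity to a delay before surgery.** Section 4.1 dates enrolment at eligibility confirmation, and screening is done at the consultation, so some delay is likely. The documents give no figure. With an assumed lag of 1 or 2 months and E = 18, the share becomes 1/18 = 5.6% (about 9 of 160) or 2/18 = 11.1% (about 18 of 160), again only if the study stopped at month 24.

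**5. Study length needed to observe everyone (no lag).**

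| Enrolment | To month 6 | To month 12 |
|---|---|---|
| 12–18 months | 18–24 months | 24–30 months |
| 24 months | 30 months | 36 months |

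**The case against.** The strongest reply concerns the calendar. A reader might infer that a quarter of the patients will lose the 6-month primary outcome. The documents do not support that:

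- Two years is an expectation, stated as approximate, and Section 8.6 makes it depend on patient availability.
- Section 4.11 closes accrual when the target number is reached, not on a date.
- Section 4.12 defines completion participant by participant, and Section 4.13 requires reasonable cause for early termination.
- Slow accrual would therefore lengthen the study. The body text also agrees with itself for this outcome (18 + 6 = 24), which points to the Summary entry as the likely error.

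Three further inferences also fail. First, 25% exceeds the 20% attrition allowance in Section 6, but the sample size there rests on the number of glands identified, which is recorded during surgery. Late calendar loss would not touch it. Second, the same formula with F = 12 gives 33% (53 of 160) for 18-month enrolment and 50% (80 of 160) for 24-month enrolment. These are not the cause of the 2.3.13 problem, because scheduled follow-up ends at month 6 even where the calendar would allow twelve months. Third, the label of primary completion is attached to the end of enrolment, before 2.2.3 has matured for everyone. However, no analysis or data lock is tied to that milestone.

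On 2.3.13, one could say that the 6-month visit already records repeat surgery. It does, up to that visit and where high calcium was the reason. If the time frame is read as the time at which a cumulative count is taken, the visit supplies the count to month 6, and months 6–12 remain uncollected. If it is read as the period in which reoperations count, the earlier ones fall outside it. The mismatch stands on both readings. So does the contradiction between the two enrolment periods.

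**Conclusion.** The mismatch in 2.3.13 is certain from the text and needs no assumption: the plan schedules no observation of months 6–12 for any patient. If it is followed as written, the trial cannot report repeat surgery over the stated window.

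The enrolment contradiction is real but smaller. With 12–18 months of enrolment the 6-month primary outcome fits, with nothing to spare at 18 months. A loss of about 25% needs 24-month enrolment, uniform accrual and an actual closure at month 24. The last of these is not in the documents, so this is a conditional risk. It would concern 2.2.3 and not the other two primary outcomes, which are read during surgery and at 5–14 days. Late entrants would come from both randomised arms, so the main cost would be precision.

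**What to change.** 1. **Align 2.3.13 with follow-up**, in one of two ways:
   - Add a chart check for repeat surgery at 12 months, and amend the Follow-Up Visits text and the off-study definition in Section 4.1 to allow it. This needs no new visits, but it does need chart review and an IRB-approved amendment (Section 7.7), possibly with reconsent. The expected study length becomes 24–30 months for 12–18 months of enrolment.
   - Restate 2.3.13 as repeat surgery up to 6 months. This changes wording only and keeps the study within 18–24 months, but later reoperations are not counted.
2. **Correct the Protocol Summary** so that its enrolment period agrees with the 12–18 months in the Primary Completion paragraph.
3. **Define study end** in Section 3.2 as the last patient's surgery plus the longest outcome window, in place of a calendar estimate. This also absorbs any delay between enrolment and surgery.

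Items 2 and 3 are edits to text and can go in the same amendment.
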